9 PRIVACY AND CONFIDENTIALITY

9.1 Privacy protections. Describe the steps you will take, if any, to address possible privacy concerns of subjects and potential subjects.

Privacy refers to the sense of being in control of access that others have to ourselves. This can be an issue with respect to recruiting, consenting, sensitivity of the data being collected, and the method of data collection.

Examples:

- Many subjects will feel a violation of privacy if they receive a letter asking them to participate in a study because they have _____ medical condition, when their name, contact information, and medical condition were drawn from medical records without their consent. Example: the IRB expects that "cold call" recruitment letters will inform the subject about how their information was obtained.
- Recruiting subjects immediately prior to a sensitive or invasive procedures (e.g., in an outpatient surgery waiting room) will feel like an invasion of privacy to some individuals.
- Asking subjects about sensitive topics (e.g. details about sexual behavior) may feel like an invasion of privacy to some individuals.

Some questions may feel intrusive to some subjects. Some questions may be embarrassing or awkward to read or answer. Subjects may choose not to answer questions that make them feel uncomfortable.

9.2 Identification of individuals in publications and presentations. Do you plan to use potentially identifiable information about subjects in publications and presentations, or is it possible that individual identities could be inferred from what you plan to publish or present?

No

Yes → If yes, will you obtain subject consent for this use?

Yes

No → If no, describe the steps you will take to protect subjects (or small groups of subjects) from being identifiable.

9.3 State mandatory reporting. Each state has reporting laws that require some types of individuals to report some kinds of abuse, and medical conditions that are under public health surveillance. These include:

- Child abuse
- Abuse, abandonment, neglect, or financial exploitation of a vulnerable adult
- Sexual assault
- Serious physical assault
- Medical conditions subject to mandatory reporting (notification) for public health surveillance

Are you or a member of your research team likely to learn of any of the above events or circumstances while conducting your research AND feel obligated to report it to state authorities?

No

Yes → If yes, the UW IRB expects you to inform subjects of this possibility in the consent form or during the consent process, unless you provide a rationale for not doing so:

9.4 Retention of identifiers and data. Check the box below to indicate your assurance that you will not destroy any identifiers (or links between identifiers and data/specimens) and data that are part of your research records until after the end of the applicable records retention requirements (e.g. Washington State; funding agency or sponsor; Food and Drug Administration) for your research. If you think it is important for your specific study to say something about destruction of identifiers (or links to identifiers) in your consent form, state something like "the link between your identifier and the research data will be destroyed after the records retention period required by state and/or federal law."

This question can be left blank for conversion applications (existing paper applications that are being "converted" into a Zipline application.)

See the "Research Data" sections of the following website for UW Records management for the Washington State research records retention schedules that apply in general to the UW (not involving UW Medicine data):

<http://f2.washington.edu/fm/recmgt/gs/research?title=R>

See the "Research Data and Records" information in Section 8 of this document for the retention schedules for UW Medicine Records: <http://www.uwmedicine.org/about/Documents/UWMRRS-1.5.pdf>

Confirm

9.5 Certificates of Confidentiality. Do you have or, are you planning to obtain, a federal Certificate of Confidentiality for your research data?

No

Yes

9.6 Data and specimen security protections. Identify your data classifications and the security protections you will provide, referring to the [ZIPLINE GUIDANCE: Data and Security Protections](#) for the minimum requirements for each data classification level. *You cannot answer this question without reading this document. Data security protections should not conflict with records retention requirements.*

a. Which level of protections will you apply to your data and specimens? If you will use more than one level, describe which level will apply to which data and which specimens.

We will apply Level 3 protections.

b. Use this space to provide additional information, details, or to describe protections that do not fit into one of the levels.

10 RISK / BENEFIT ASSESSMENT

10.1 Anticipated risks. Describe the reasonably foreseeable risks of harm, discomforts, and hazards to the subjects and others of the research procedures. For each harm, discomfort, or hazard:

- Describe the magnitude, probability, duration, and/or reversibility of the harm, discomfort, or hazard, AND
- Describe how you will manage or reduce the risks. Do not describe data security protections here, these are already described in Question 9.6.

- Consider physical, psychological, social, legal, and economic risks, including risks to financial standing, employability, insurability, educational advancement or reputation.
- Examples of "others": embryo, fetus, or nursing child; family members; a specific group.
- Do not include the risks of non-research procedures that are already being performed.
- If the study design specifies that subjects will be assigned to a specific condition or intervention, then the condition or intervention is a research procedure - even if it is a standard of care.
- Examples of mitigation strategies: inclusion/exclusion criteria; applying appropriate data security measures to prevent unauthorized access to individually identifiable data; coding data; taking blood samples to monitor something that indicates drug toxicity.
- As with all questions on this application, you may refer to uploaded documents.

We have (a) developed and implemented the [Return to In-Person Research Plan](#) and (b) completed all of the relevant activities listed on the [CHECKLIST Human Subjects Research During the COVID-19 Pandemic](#).

Risks of Participating in Behavioral Intervention: Subjects may experience embarrassment or discomfort from discussing personal information about food, eating habits, body image, or exercise. Dietary change, exercise, and weight loss may pose special risks for those with specific comorbid medical conditions. There is some risk to initiating an exercise program, including revealing unknown health or cardiac disease or becoming injured. Making lifestyle changes can be difficult and frustrating, and weight regain after an intervention can be discouraging.

2. Study Procedures. Potential risks include 1) anxiety and embarrassment as a result of completing the medical history, physical examination, or other self-reported measures; 2) pain, minor injury (bruising), or the development of a localized inflammation (thrombophlebitis) from obtaining blood samples. Occasionally people feel faint or nauseous during blood draw; 3) intake of a mandatory amount of a standardized snack that may in rare cases cause discomfort, nausea, vomiting, or a reaction from an unidentified food allergy or sensitivity; and 4) discomfort from hunger due to fasting or hypoglycemia due to fasting.

DXA scan: There are some risks from the DXA scan you will undergo during this study. This scan will expose you to radiation. If you live in the US, you receive about 3 millisieverts of radiation each year. It comes from space and the earth around you. This is called “background radiation.” A “millisievert” (mSv) is a unit used to measure doses of radiation. The radiation dose to your whole body from your DXA scan will be less than 0.01 mSv. The risk of harm from this amount of radiation is very low. If you have more procedures that expose you to radiation, this risk will go up. The radiation from x-rays and scans may be harmful to a fetus. If you are a woman who could become pregnant, you must have a pregnancy test done before your DXA scan. If you are pregnant you may not take part in this study.

3. *Symptomatic Hypotension*: Weight loss may reduce blood pressure.

4. *MRI scanning*. The risks associated with MRI are extremely low, and no invasive procedures or intravenous contrast agents are included in this procedure. Risks include the possibility that undetected metal in the subject's body could be displaced by the magnetic field of the MRI scanner. Participants could become claustrophobic while in the scanner. Participants could experience discomfort in attempting to remain still for up to 60 minutes in the scanner. Subjects could feel embarrassment if their body shape is a tight fit or not conducive to fitting in the MRI. The tasks could cause boredom or anxiety in some participants. Credit cards, watches, or other items could be damaged by the magnetic field if they are inadvertently brought into the scan room. Headphones and earplugs are provided to the subjects to protect subjects from scanner gradient noise. There will be no cost to the participant or the participant's insurance company for the MRI scans done specifically for this study. The scans will be paid for with funds from this grant application. However, if an incidental finding occurs, subjects may experience anxiety, and additional procedures or costs could be incurred.

5. *Breach of confidentiality*. The potential risk of DNA analysis and financial risks associated with participating in this study are due to the potential of any health information being disclosed to health or life insurance companies or to current or potential employers. While this is a potentially serious risk, it is very unlikely, as we will keep all personally identifiable information physically separate from all health information. All information will be on password-protected computers or in locked file cabinets in locked offices.

6. Hygiene procedures due to COVID-19. We will comply with cleaning procedures for space and equipment required by HSD and UW. This will also apply to equipment that may be touched or used by multiple participants.

10.2 Reproductive risks. Are there any risks of the study procedures to men and women (who are subjects, or partner of subjects) related to pregnancy, fertility, lactation or effects on a fetus or neonate?

Examples: direct teratogenic effects; possible germline effects; effects on fertility; effects on a woman's ability to continue a pregnancy; effects on future pregnancies.

No → If no go to [question 10.3](#)

Yes → If yes, answer the following questions:

a. Risks. Describe the magnitude, probability, duration and/or reversibility of the risks.

This study includes DXA scan as a procedure. Female subjects will be given a pregnancy test prior to having a DXA scan. Pregnant subjects will not be eligible to participate.

b. Steps to minimize risk. Describe the specific steps you will take to minimize the magnitude, probability, or duration of these risks.

Examples: inform the subjects about the risks and how to minimize them; require a pregnancy test before and during the study; require subjects to use contraception; advise subjects about banking of sperm and ova.

If you will require the use of contraception: describe the allowable methods and the time period when contraception must be used.

Female subjects will have a pregnancy test prior to the DXA scans.

c. Pregnancy. Describe what you will do if a subject (or a subject's partner) becomes pregnant

For example; will you require the subject to immediately notify you, so that you can discontinue or modify the study procedures, discuss the risks, and/or provide referrals or counseling?

If a subject becomes pregnant they will not be able to continue with the study. Subjects will have pregnancy tests prior to having a DXA scan. We will ask subjects to notify research staff if they become pregnant.

10.3 Unforeseeable risks. Are there any research procedures that may have risks that are currently unforeseeable?

Example: using a drug that hasn't been used before in this subject population.

	No
	Yes

→ If yes, identify the procedures.

10.4 Subjects who will be under regional or general anesthesiology. Will any research procedures occur while subjects-patients are under general or regional anesthesia, or during the 3 hours preceding general or regional anesthesia (supplied for non-research reasons)?

	No
	Yes

→ If yes, check all the boxes that apply.

- Administration of any drug for research purposes
- Inserting an intra-venous (central or peripheral) or intra-arterial line for research purposes
- Obtaining samples of blood, urine, bone marrow or cerebrospinal fluid for research purposes
- Obtaining a research sample from tissue or organs that would not otherwise be removed during surgery
- Administration of a radio-isotope for research purposes**
- Implantation of an experimental device
- Other manipulations or procedures performed solely for research purposes (e.g., experimental liver dialysis, experimental brain stimulation)

If you checked any of the boxes:

You must provide the name and institutional affiliation of a physician anesthesiologist who is a member of your research team or who will serve as a safety consultant about the interactions between your research procedures and the general or regional anesthesia of the subject-patients. If your procedures will be performed at a UW Medicine facility or affiliate, the anesthesiologist must be a UW faculty member.

*** If you checked the box about radio-isotopes: you are responsible for informing in advance all appropriate clinical personnel (e.g., nurses, technicians, anesthesiologists, surgeons) about the administration and use of the radio-isotope, to ensure that any personal safety issues (e.g., pregnancy) can be appropriately addressed. This is a condition of IRB approval.*

10.5 Data and Safety Monitoring. A Data and Safety Monitoring Plan (DSMP) is required for clinical trials (as defined by NIH). If required for your research, upload your DSMP to the Supporting Documents SmartForm in **Zipline**. If it is embedded in another document you are uploading (for example, a Study Protocol, use the text box below to name the document that has the DSMP.

This study will have a Safety Monitor. We will upload the DSMP to Zipline.

10.6 Un-blinding. If this is a double-blinded or single-blinded study in which the participant and/or you do not know the group to which the participant is assigned: describe the circumstances under which un-blinding would be necessary, and to whom the un-blinded information would be provided.

N/A

10.7 Withdrawal of participants. If applicable, describe the anticipated circumstances under which participants will be withdrawn from the research without their consent. Also, describe any procedures for orderly withdrawal of a participant, regardless of the reason, including whether it will involve partial withdrawal from procedures and any intervention but continued data collection or long-term follow-up.

No anticipated circumstances where subjects will be withdrawn without their consent.

10.8 Anticipated direct benefits to participants. If there are any direct research-related benefits that some or all individual participants are likely to experience from taking part in the research, describe them below:

Do not include benefits to society or others, and do not include subject payment (if any). Examples: medical benefits such as laboratory tests (if subjects receive the results); psychological resources made available to participants; training or education that is provided.

The subjects may lose and may maintain weight loss, both of which would benefit their health. No results will be routinely shared with subjects.

10.9 Individual subjects findings.

a. Is it likely that your research will unintentionally discover a previously unknown condition such as a disease, suicidal intentions, or genetic predisposition?

No

Yes → If yes, explain whether and how you would share the information with the subject.

It is possible that an abnormality in labs or MRI could be discovered. The Principal Investigator will contact the subject and advise them to see a physician to follow up on the abnormal finding.

b. Do you plan to routinely share the individual results of your study procedures with the subjects – such as genetic test results, laboratory tests, etc.?

No

Yes → If yes, complete and upload the [SUPPLEMENT: Participant Results Sharing](#) to the Supporting Documents SmartForm of *Zipline*

10.10 Commercial products or patents. If a commercial product or patent could result from this study, describe whether subjects might receive any remuneration/compensation and, if yes, how the amount will be determined:

N/A

11 ECONOMIC BURDEN TO PARTICIPANTS

11.1 Financial responsibility for research-related injuries. Answer this question only if the lead researcher is not a UW student, staff member, or faculty member whose primary paid appointment is at the UW.

Describe who will be financially responsible for research-related injuries experienced by subjects, and any limitations. Describe the process (if any) by which participants may obtain treatment/compensation.

N/A

11.2 Costs to subjects. Describe any research-related costs for which subjects may be responsible (e.g., CT scan required for research eligibility screening; co-pays; cost of a device; travel and parking expenses that will not be reimbursed).

Prior to MRI, if a hobby or job or incident involving exposure to metal fragments is mentioned during MRI screening, the MRI staff may require an x-ray prior to scanning. We would ask the subject if they are willing to do this in order to participate. The study will not pay for the procedure. If the subject refuses, they will not participate in the study as MRIs are an important part of the study.

11.3 Reimbursement for costs. Describe any costs to subjects that will be reimbursed (such as travel expenses).

None.

12 RESOURCES

12.1 Faculty Advisor. (For researchers who are students, fellows, or post-docs.) Provide the following information about your faculty advisor.

- Advisor's name
- Your relationship with your advisor (for example: graduate advisor; course instructor)
- Your plans for communication/consultation with your advisor about progress, problems, and changes.

N/A

12.2 Study team communication. Describe how you will ensure that each study team member is adequately trained and informed about the research procedures and requirements (including any changes) as well as their research-related duties and functions.

There is no study team.

The research team will have weekly meetings to review progress and changes that need to be implemented. All staff will have appropriate credentials and training for work in research with human subjects.

13 OTHER APPROVALS, PERMISSIONS, and REGULATORY ISSUES

13.1 Other regulatory approvals. Identify any other regulatory approvals that are required for this research, by checking applicable boxes

Do not attach the approvals unless requested by the IRB.

Approval	Research for which this is required
 Radiation Safety	Procedures involving the use of radioactive materials or an ionizing radiation producing machine radiation, if they are conducted for research rather than clinical purposes. Approvals need to be attached to the Supporting Documents page in Zipline .
 Institutional Biosafety	Procedures involving the transfer/administration of recombinant DNA, DNA/RNA derived from recombinant DNA, or synthetic DNA.
 RDRC	Procedures involving a radioactive drug or biological product that is not approved by the FDA for the research purpose and that is being used without an IND, for basic science research (not to determine safety and effectiveness, or for immediate therapeutic or diagnostic purposes).
 ESCRO	Procedures involving the use of some types of human embryonic stem cells.

13.2 Approvals and permissions. Identify any other approvals or permissions that will be obtained. For example: from a school, external site/organization, funding agency, employee union, UW Medicine clinical unit.

Do not attach the approvals and permissions unless requested by the IRB.

Regarding COVID-19 requirements, we have developed a Return to In-Person Research Plan. We will complete all HSD required points on the checklist for research during COVID-19

13.3 Financial Conflict of Interest. Does any member of the team have a Financial Conflict of Interest (FCOI) in this research, as defined by [UW policy GIM 10](#)?

	No
	Yes

→ If yes, upload the Conflict Management Plan for every team member who has a FCOI with respect to this research, to the Supporting Documents page of **Zipline**. If it is not yet available, use the text box to describe whether the Significant Financial Interest has been disclosed already to the UW Office of Research.

A Cohort Study of Weight Loss and Gliosis

NCT0357887

6/9/2025

Statistical Analysis Plan

Weight loss will be determined by the percentage change in weight during the 6-month behavioral weight loss program. For all participants, weight change will be calculated as weight at 6-months minus weight at baseline, as a percentage. Weight regain will be considered during the 12-month follow up period. Change in kilograms of weight will be calculated from the 18-month visit minus weight at the 6-month visit. Weight change outcomes will be tested by One-way ANOVA with Bonferroni correction for multiple comparisons. P-values less than 0.05 will be considered significant. Analyses will be unadjusted.

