HSD may ask for documentation of the externally-imposed urgency. A higher priority should not be requested to compensate for a researcher's failure to prepare an IRB application in a timely manner. Note that IRB review requires a certain minimum amount of time; without sufficient time, the IRB may not be able to review and approve an application by a deadline.

No

Yes → If yes, briefly describe the urgency or deadline as well as the reason for it.

We have received a just-in-time request from NIH for this application.

1.5 Objectives Using lay language, describe the purpose, specific aims, or objectives that will be met by this specific project. If hypotheses are being tested, describe them. You will be asked to describe the specific procedures in a later section.

If your application involves the use of a HUD "humanitarian" device: describe whether the use is for "on-label" clinical patient care, "off-label" clinical patient care, and/or research (collecting safety and/or effectiveness data).

1. To determine in obese humans undergoing Behavioral Weight Loss whether the severity of hypothalamic gliosis at baseline predicts the degree of weight loss in treatment and/or maintenance of weight loss over time
2. To test in obese humans whether larger weight losses are associated with greater improvements in hypothalamic gliosis and if RYGB/sleeve gastrectomy (may be referred to as bariatric surgery in this application) provides an added benefit for reducing gliosis.

1.6 Study design. Provide a one-sentence description of the general study design and/or type of methodology.

Your answer will help HSD in assigning applications to reviewers and in managing workload. Examples: a longitudinal observational study; a double-blind, placebo-controlled randomized study; ethnographic interviews; web scraping from a convenience sample of blogs; medical record review; coordinating center for a multi-site study.

A longitudinal observational study of patients before and after weight loss via lifestyle change or bariatric surgery. The lifestyle program is part of this research and the surgery patients are a clinical population undergoing surgery at UW.

1.7 Intent. Check all the descriptors that apply to your activity. You must place an "X" in at least one box.

This question is essential for ensuring that your application is correctly reviewed. Please read each option carefully.

Descriptor

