The long-term health benefits of obesity treatment are limited by the weight regain that almost universally follows a weight loss intervention, frustrating patients and clinicians alike. In lay terms, a new, higher “set point” seems to occur after people gain weight, and research shows that processes of energy homeostasis, directed by neurons in the arcuate nucleus of the hypothalamus, vigorously defend the higher level of adiposity for years, promoting weight regain after behavioral weight loss. Bariatric surgery, however, results in weight loss that is more durable over time. These phenomena remain incompletely understood. The current proposal endeavors to address this crucial scientific gap by investigating the brain’s role in the persistence of obesity and weight regain after weight loss. Specifically, studies in rodents show that diet-induced weight gain requires an inflammatory and cellular response, known as gliosis, within the arcuate nucleus of the hypothalamus and that this gliosis persists with continued dietary exposure. Importantly, gliosis is detectable in mice and humans by magnetic resonance imaging (MRI). Using MRI, the investigators discovered the first evidence of hypothalamic gliosis in obese humans. The investigators have also shown that hypothalamic gliosis is improved by Roux-en-Y gastric bypass (RYGB) or sleeve gastrectomy surgery, suggesting that the efficacy and durability of weight loss via bariatric surgery could be partially explained by its ability to reverse gliosis. New findings show that hypothalamic gliosis negatively impacts brain regulation of appetite. Based on such findings, the proposed research investigates novel questions about the possible implications of hypothalamic gliosis for clinical weight management. First, it will determine whether the extent of hypothalamic gliosis present when people with obesity start a behavioral weight loss program is related to their success in treatment or weight regain after treatment. Second, the current proposal also addresses the question of whether gliosis is reduced to a greater extent when weight loss occurs by RYGB or sleeve gastrectomy than by lifestyle change alone. Finally, this investigation uses a rodent study to test the role of 2 different hypothalamic glial cell types in weight regain after weight loss. In sum, basic science advances have identified hypothalamic cellular responses that facilitate weight gain during times of nutritional abundance, but this biological process is also capable of forming glial scars that are detrimental to neuronal functioning. The current research therefore investigates the implications of hypothalamic gliosis for humans undergoing obesity treatment. Achieving a better understanding of the role of the brain in successful obesity treatment could open new avenues for research, intervention, and prevention to alleviate the health risks of obesity.

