2 PARTICIPANTS

2.1 Participants. Describe the general characteristics of the subject populations or groups, including age range, gender, health status, and any other relevant characteristics.

Three groups of subjects will include males and females aged 21-64.

1. Healthy weight controls (HWC)

2. Obese, Lifestyle Cohort (Behavioral Weight Loss, BWL)
3. Obese, Surgical Cohort or Surgical Weight Loss (SWL) (RYGB or sleeve gastrectomy)

2.2 Inclusion and exclusion criteria. Describe the specific criteria you will use to decide who will be included in your study from among interested or potential subjects. Define any technical terms in lay language.

Inclusion Criteria: At the time of screening:

HWC: BMI 18.5-24.9 kg/m²,

BWL: BMI 30-<56 kg/m²,

Bariatric: BMI 30-<56 kg/m², eligible for RYGB or sleeve gastrectomy and not undergoing revision or reoperation.

Exclusion Criteria:

- Poorly controlled hypertension or coronary artery disease, or chronic disease (e.g. cancer, multiple sclerosis, autoimmune disease, rheumatic disease)
 - Blood Pressure > 160/100 mmHG
 - Heart Rate > 110 bpm
- Chronic kidney disease (GFR <60 mL/min/1.73 m²),
- Presence of cirrhosis (NALFD/NASH are acceptable),
- Previous or planned (during the study period) obesity treatment with surgery (planned surgery ok for the SWL group) or a weight loss device. However, the following are allowed: (1) liposuction and/or abdominoplasty, if performed > 1 year before screening, (2) lap banding, if the band has been removed > 1 year before screening, (3) intragastric balloon, if the balloon has been removed > 1 year before screening or (4) duodenal-jejunal bypass sleeve, if the sleeve has been removed > 1 year before screening,
- A1c > 8.5% in Bariatric group; A1c ≥ 6.5% for BWL and HWC groups,
- Current use of insulin (insulin ok for Surgical Weight Loss group, also called SWL), DPP-4 inhibitors, thiazolidinediones or medications known to alter metabolic function (e.g. atypical antipsychotics, corticosteroids),
- Pregnancy or breastfeeding,
- MRI contraindications (e.g. implanted metal, claustrophobia), or unable to have MRI or fit in MRI scanner
- Current smoking/daily use of nicotine containing products (cigarettes, e-cigarettes, vaping or other nicotine containing products) or heavy alcohol use,
- Weight >450 pounds (iDXA limit),
- Weight-reduced from lifetime maximum weight by >16% (BWL and HWC only),
- Weight not stable over past 3 months (±10% BWL and HWC, ±15% SWL)
- T2D (for BWL or HWC),

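### The SAP specifies no gliosis analysis: surgery's added benefit cannot be tested under it, the other two gliosis questions have no stated test, and its unadjusted rule does not suit a surgery contrast

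*SAP*

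**What the plan says.** **SAP.** The body is seven sentences. It defines two outcomes: percentage weight change from baseline to 6 months, and weight change in kilograms from 6 to 18 months. Its only test reads "Weight change outcomes will be tested by One-way ANOVA with Bonferroni correction for multiple comparisons". No ANOVA factor is named. Significance is set at 0.05, and the plan closes with "Analyses will be unadjusted". Gliosis appears only in the title.

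**Protocol, section 1.5 (Objectives).** Aim 1, in the lifestyle cohort (BWL), asks "whether the severity of hypothalamic gliosis at baseline predicts the degree of weight loss in treatment and/or maintenance of weight loss over time". Aim 2 asks "whether larger weight losses are associated with greater improvements in hypothalamic gliosis", and also whether bariatric surgery "provides an added benefit for reducing gliosis". Section 1.8a restates this last question as "whether gliosis is reduced to a greater extent when weight loss occurs by RYGB or sleeve gastrectomy than by lifestyle change alone".

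**Protocol, section 5.1.** The visit table schedules gliosis MRI at baseline, the weight-change visit, and 6, 12 and 18 months. Section 1.8a places the gliosis in the arcuate nucleus. Neither document gives the exact region of interest, the sequence or the metric, and the protocol has no statistics section.

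**Protocol, section 2.2.** Eligibility differs between the surgical cohort (SWL) and BWL. One exclusion reads "A1c > 8.5% in Bariatric group; A1c ≥ 6.5% for BWL and HWC groups"; the others are set out in the check below.

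**The concern.** A plan that tests only weight cannot report on aims about gliosis. With no gliosis measure or model stated, the metric, the form of the model, the covariates and the scope of the multiplicity correction could all be chosen after the data are seen. That freedom matters more here than in a randomised trial, because in a cohort comparison the choice of model and comparison set can drive the answer.

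The one modelling rule that the SAP does state points the wrong way for the surgery question. An unadjusted SWL-versus-BWL contrast in gliosis change would mix any effect of surgery with differences that the eligibility criteria build in.

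**Working it through.** No figure in the documents bears on this point, so the check sets the texts side by side.

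**Step 1. What the SAP body contains.** A count of terms in its seven sentences finds weight 10 times. Gliosis, MRI, brain, hypothalamus, surgery, bariatric, group, association, correlation, regression and prediction each occur 0 times. The text shows no redaction that would explain this.

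**Step 2. What each question needs against what the SAP gives.**

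| Question (section 1.5) | Outcome needed | Predictor needed | SAP gives |
|---|---|---|---|
| Aim 1 | Weight change to 6 months; weight change from 6 to 18 months | Baseline gliosis | Both outcomes; no predictor; no test of it |
| Aim 2, association | Change in gliosis | Weight loss | Weight change only; no gliosis outcome; no test |
| Aim 2, added benefit of surgery | Change in gliosis | SWL versus BWL | No gliosis outcome; a test on a different variable |

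In the third row the outcome itself is missing from the plan. Whatever factor the ANOVA uses, a comparison of weight change cannot show whether gliosis fell more. In the second row nothing relates the two variables. In the first row the plan is incomplete but not incompatible with the aim.

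**Step 3. Whether an unadjusted rule suits the surgery contrast.** From section 2.2:

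| Criterion | BWL | SWL |
|---|---|---|
| Type 2 diabetes | Excluded | Not excluded |
| Current insulin | Excluded | Allowed |
| A1c | Excluded at 6.5% or above | Excluded only above 8.5% |
| Weight stability, past 3 months | Within 10% | Within 15% |
| More than 16% below lifetime maximum weight | Excluded | Exclusion not applied |
| Currently in a weight loss program | Excluded | Allowed, subject to weight-history conditions |
| BMI | 30 to below 56 | 30 to below 56 |

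Six criteria differ and BMI does not. The conditions in the sixth row refer to the lifetime-maximum rule, which the fifth row's criterion confines to BWL and healthy controls. The extent of the SWL exemption is therefore not fully clear for participants enrolled in a program.

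**Step 4. Whether covariates alone would repair it.** Diabetes does not occur in BWL by design, and A1c from 6.5% to 8.5% is admitted only in SWL. A regression term for diabetes would be estimated wholly within SWL, and its use to correct the cohort contrast would be extrapolation. Restricting the comparison to participants who could have entered either cohort on these criteria avoids that step.

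**The case against.** **The documents may not be the whole plan.** The protocol is an ethics application, written partly in lay language, and it mentions NIH funding; a grant text could hold the imaging measure and the gliosis models. This stands as a limit. A reader might infer that the investigators have no gliosis measure or analysis at all, and the documents do not support that. What they show is that the SAP neither confines itself to weight outcomes nor points to another analysis document.

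**The ANOVA factor could be categories of baseline gliosis.** That is conceivable and would reach Aim 1, so it would be too strong to say that Aim 1 cannot be tested. But no such factor or cut-points are stated. With weight change defined for all participants, three cohorts and a Bonferroni correction, cohort is the natural reading. Even the favourable reading leaves Aim 2 without an analysis.

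**Unadjusted analysis can be legitimate.** For prediction within one cohort it is. The objection to the unadjusted rule is therefore confined to the surgery contrast.

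**Further inferences that do not hold.** A reader might add BMI to the built-in differences, but its eligibility range is the same in both cohorts. A reader might also say that the surgical baseline scan is mistimed. The day or two before surgery in section 5.1 is only an example of why the activity monitor may be optional, and it does not set scan timing. Nor do the documents show that the study is too small: neither gives a power, effect size or standard deviation.

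**Conclusion.** The point holds and should be fixed before gliosis results are reported. Followed exactly as written, the SAP gives no result on surgery's added benefit for gliosis, no pre-specified test of the Aim 2 association, and an incomplete Aim 1. None of the three gliosis questions has a complete stated analysis.

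The unadjusted rule is unsuited to an SWL-versus-BWL gliosis contrast because the cohorts are not randomised and six eligibility criteria differ. The documents do not show the size or direction of the resulting bias.

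The conclusion rests on the two supplied documents and on no numerical assumption.

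**What to change.** Revise the SAP, date the revision, and state what data had been examined by then.

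- **Measure.** Define the MRI gliosis variable: region of interest, sequence and metric.
- **Aim 1, BWL only.** Regress 6-month percentage weight change, and separately 6-to-18-month weight change, on continuous baseline gliosis.
- **Aim 2, association.** Model 6-month gliosis change on percentage weight loss in the two cohorts with obesity.
- **Aim 2, surgery.** Model 6-month gliosis change on SWL versus BWL, adjusted for baseline gliosis. Report it without and with weight loss in the model, and note that weight loss is a post-treatment variable.
- **Adjustment rule.** Replace the blanket unadjusted statement for these models.
- **Eligibility differences.** Pre-specify an analysis restricted to SWL participants who also meet the BWL criteria for diabetes, A1c, insulin, weight stability and reduction from lifetime maximum weight. Do not rely on covariate adjustment for diabetes. State that residual confounding remains, including from enrolment in a weight loss program.
- **Multiplicity and weight.** State which tests the Bonferroni correction covers. Name the ANOVA factor, and keep the cohort comparison of weight as secondary.

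The change is to SAP text only. The MRI scans, weights, medical history and screening values are already part of the study. The costs are more analysis work, including settling the gliosis measure, and a restricted analysis with fewer surgical participants than the planned maximum of 35. A1c in SWL may come from medical records of differing date: section 4.1 allows extraction of blood values from the record, and section 5.7 allows pre-screening laboratory data up to 6 months old. The restriction should therefore state which A1c value it uses.
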